While we have essentially kept the pre-post evaluation format as per the approved MI4 proposal we have decided to improve the research design by adding a control condition, therefore making this a randomized controlled trial. The full research proposal that has been submitted to the McGill Interdisciplinary Initiative in Infection and Immunity (MI4) and approved for funding is attached in section 13 "Other document" on Nagano (F11P-20611).

Methods

Sample

A survey will be administered online to a sample of Canadian residents aged 20-39 years old in both English and French. Our only exclusion criterion is having received any number of doses of any currently available COVID-19 vaccine. A sample of 2,630 participants will be drawn from a database panel provided by Dynata, the world's largest first-party data and insight

platform, to complete the survey. Dynata's use of Canadian census data from Statistics Canada and quota-based sampling will ensure that the sample will closely match the Canadian population in terms of sex, first language English/French, population density (i.e. urban vs. rural), and household income.

To calculate the required sample size for the within-participant change in vaccine hesitancy (i.e., pre-post intervention) we used the latest survey data showing that approximately 40% of Canadians in this age group are COVID-19 vaccine hesitant i.e., don't know yet or would refuse vaccination. Estimating a 5% decrease of hesitancy in the intervention group and a correlation of about 0.45 between paired observations, the intervention group requires a sample size of 1315 pairs for detecting a 5% change of marginal proportions at a power of 80% and two-sided significance of 5%.

We will use 1:1 randomization of participants. Thus, 50% will be allocated to the intervention and 50% to the control group. Using equal size groups will allow us to detect a between group difference in vaccine intentions of 5-6% with a power of 0.8 and a two-sided significance of 5%. The total sample required for this study is 2630 participants i.e., 1315 in the intervention group and 1315 in the control group.

Recruitment Strategy

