be asked whether they consent to taking part in the survey. Those who consent to taking part in the survey will be invited to go to the next page and start completing the survey. Participants will first be asked to answer several socio-demographic questions and will be asked to choose one of the following categories which describe their COVID-19 vaccine decision-making stage according to the Precaution Adoption Process Model (PAPM): unengaged, undecided, decided not to receive the vaccine, or decided to receive the vaccine.

Subsequently, depending on their randomly assigned condition, participants will either be shown a 2-minute altruism-eliciting video, or a brief informational text. After viewing this content, to ensure that participants paid attention, participants will answer questions about the contents to check their understanding.

Finally, participants will: 1) once again be asked to choose their COVID-19 vaccine decision-making stage; 2) be asked questions regarding previous vaccination history (e.g. seasonal influenza), lifestyle factors, self-perceived health status, personal history of SARS-CoV-2 infection, and preferred health-information channels; and 3) complete validated scales regarding altruism, empathy, personal distress, and vaccine hesitancy.

Funding

This study is funded by the McGill Interdisciplinary Initiative in Infection and Immunity (MI4) (<https://www.mcgill.ca/mi4/>). Neither the principal investigator nor the institution is in a situation of conflict of interest as a result of this funding.

Risks and Concerns

Participating in this research study has no known or serious risks. There is no evidence in the scientific literature that eliciting altruism could produce negative consequences or emotions in participants. However, it is possible that participants of the focus group may experience discomfort or upset as the result of the research intervention.

In the event that participants experience discomfort after the study procedures, they will also be provided with the link to a governmental website where they will find available resources in their regions: <https://www.canada.ca/en/public-health/services/mental-health-services/mental-health-get-help.html>.

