Document Cover Page

Full Analysis Plan

Study Title:

Enhancing COVID-19 Vaccination Intentions by Eliciting Prosocial Altruistic Motives:
Evaluating the Efficacy of a Brief Video-Based Intervention

NCT number: NCT04960228

Date of Document: February 5th, 2022

Analysis Plan

Sociodemographics

For baseline sociodemographics we calculated proportions, means (and standard deviation, SD) and used the Pearson Chi-Squared Test and the Welch two sample t-test to evaluate if the two study groups differed significantly.

Objectives 1 and 2.

At baseline and post-intervention and for each of the study groups we calculated the proportion of participants in each of the four PAPM intention stage i.e., *unengaged*, *undecided*, *decided not*, and *decided to*. For each study group we calculated the pre-to post transitions in intentions to receive the COVID-19 vaccine. To estimate the pre-to-post intervention change in vaccine intentions we used a binary outcome (i.e., Vaccine intenders corresponding to the stage *decided to*; and Vaccine non-intenders that included stages *unengaged*, *undecided*, and *decided not*) and the McNemar's Chi-squared test. Post intervention, we estimated the between group difference in vaccine intentions using the four-stage PAPM outcome and the Pearson Chi-Squared Test.

Exploratory Analyses with PAPM stages

To estimate pre to post changes in PAPM intention stages we conducted exact tests of symmetry (4x4 contingency tables) that comprise pairwise McNemar tests (using the “nominalSymmetryTest” function available in the R package “rcompanion”) (1). For each study group we used the significant transitions between vaccine intention stage pairs for calculating the total number of participants that changed towards increased vaccination intentions (e.g., from *undecided* to *decided to*) and estimated the between-group difference using the Chi-squared two-sample test for equality of proportions.

All statistical analyses were conducted using the R software v. 4.0.5.(2).

References

1. Mangiafico S. Package 'rcompanion' 2022 [Available from: <https://cran.r-project.org/web/packages/rcompanion/rcompanion.pdf>].
2. R Development Core Team. R: A Language and Environment for Statistical Computing. R Foundation for Statistical Computing Vienna, Austria 2005 [Available from: <http://www.R-project.org/>].

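### The between-arm test ignores the baseline vaccination stage, which costs power and leaves no pre-specified randomised estimate among hesitant participants if the video works mainly by converting them.

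*Protocol*

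**What the plan says.** - **Who is enrolled.** Protocol, efficacy study, Sample: "Our only exclusion criterion is having received any number of doses of any currently available COVID-19 vaccine". The panel quotas there, and the randomisation strata under Procedure, are first language, sex, population density and household income. Vaccination intention is in neither list.
- **Planning figures.** The same section takes "approximately 40% of Canadians in this age group are COVID-19 vaccine hesitant", meaning undecided or refusing. It sizes the pre-post comparison by "Estimating a 5% decrease of hesitancy in the intervention group and a correlation of about 0.45 between paired observations". For the randomised comparison, with 1315 per arm, it says: "Using equal size groups will allow us to detect a between group difference in vaccine intentions of 5-6% with a power of 0.8".
- **When stage is measured.** Procedure: before the content, participants choose among "unengaged, undecided, decided not to receive the vaccine, or decided to receive the vaccine". The question is asked again afterwards.
- **Between-arm test.** SAP, Objectives 1 and 2: "Post intervention, we estimated the between group difference in vaccine intentions using the four-stage PAPM outcome and the Pearson Chi-Squared Test". Baseline stage does not enter it. The McNemar test in the same section is within arm.
- **Exploratory comparison.** The SAP also compares between arms the number who moved towards vaccination. It counts the transitions found significant within each group and gives no denominator.

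**The concern.** On the protocol's figure, about 60% of participants start at *decided to*, the top stage, and cannot move up. If the video works mainly by moving the other 40%, the whole-sample difference is only 0.40 times the effect among the hesitant. The planned test uses none of the baseline information that would recover the lost precision.

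Two things are at stake. A useful conversion rate among hesitant young adults could be reported as no difference between arms. And the public health users named in the protocol would have no pre-specified randomised contrast, with a confidence interval, for how many hesitant people the video persuades.

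**Working it through.** **Inputs from the protocol:** 1315 per arm; 40% hesitant; two-sided 5%; correlation 0.45; 5-point pre-post change. **Assumed, because the documents are silent:** control conversion (baseline-hesitant control participants who choose *decided to* when re-asked), ranged over 2-33%; intender loss (baseline *decided to* participants who leave that stage); no dropout.

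**Formula for two proportions, n per arm:** power = Φ{[d√n − 1.96√(2p̄(1−p̄))] / √(p0(1−p0) + p1(1−p1))}, where d = p1 − p0 and p̄ is their mean.

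**1. The plan's figure.** n = 1315, 60% v 65% intending: (1.813 − 1.342)/0.684 = 0.689, power 0.755. Solving for 80% power gives d = 5.28 points, inside the stated 5-6. At 6 points, power is 0.89. The figure reproduces on a binary contrast.

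**2. The same figure among the hesitant.** If intenders behave alike in both arms, the overall effect is 0.40 × the effect in the hesitant, and 5.28/0.40 = 13.2 points. A 7.5-point gain among the hesitant is 3 points overall: 60% v 63% has power 0.352.

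**3. Baseline hesitant only.** n = 0.40 × 1315 = 526 per arm.

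| Assumed control conversion | Detectable difference, 80% power | Power for +7.5 points |
|---|---|---|
| 2% | 3.2 points | >0.999 |
| 5% | 4.5 | 0.991 |
| 10% | 5.8 | 0.943 |
| 20% | 7.3 | 0.816 |
| 33% | 8.3 | 0.714 |

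**4. Whole sample, standardised over baseline status.** Variance = 0.4²[c0(1−c0) + c1(1−c1)]/526 + 0.6²[l0(1−l0) + l1(1−l1)]/789, where c is conversion and l is intender loss. With conversion 10% v 17.5% and loss 5% in both arms, d = 3 points, SE = 1.07 points, and power = Φ(3/1.07 − 1.96) = 0.80. Unadjusted (61% v 64%) it is about 0.355. With conversion 20% v 27.5% and loss 10%, the figures are 0.58 and 0.36.

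**5. Effect spread over both groups, as correlation 0.45 implies.**
- Control, margins stable at 40%: hesitant both times = 0.16 + 0.45 × 0.24 = 0.268. Conversion = 0.132/0.40 = 33%; loss = 0.132/0.60 = 22%.
- Video, 40% to 35%: hesitant both times = 0.14 + 0.45 × √(0.24 × 0.2275) = 0.245. Conversion = 1 − 0.245/0.40 = 38.7%; loss = (0.35 − 0.245)/0.60 = 17.5%.
- The 5-point effect is then 0.4 × 5.7 = 2.3 points from conversion plus 0.6 × 4.5 = 2.7 points from retention.
- Power: hesitant only 0.49; whole sample unadjusted 0.755; whole sample adjusted 0.84.

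**6. Exploratory mover comparison.** Counting every conversion to *decided to* over 1315 per arm, a 7.5-point gain at 10% control conversion is 4% v 7%, power 0.92. At 5, 20 and 33% it is about 0.99, 0.75 and 0.59.

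**The case against.** The strongest reply is that the plan chose its target and hit it. The stated purpose concerns young Canadians' intentions, not those of the hesitant alone. The quotas aim at a sample resembling the population, and 5-6 points is correct for that target. All of this stands. A reader might infer that the between-group sizing is wrong, and the documents do not support that.

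A reader might also infer that the roughly 60% who already intend vaccination only add noise. They do not. They can leave *decided to*, and on the plan's own correlation about 22% would do so on re-asking, so keeping them is part of the net effect. In that case the hesitant-only comparison is the weakest of the three (step 5), and it must not replace the whole-sample result.

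The exploratory mover analysis is a partial substitute and can recover much of the power (step 6). The transition tables by arm would also show the raw conversion rates. What is missing is a fixed definition: the mover analysis is exploratory, selects transitions by significance within each arm, so the two arms may count different transitions, and states no denominator. McNemar's test uses only discordant pairs and is not diluted in this way, but it does not compare video with control.

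Two further limits stand. The 40% describes the age group, while the sample excludes the vaccinated, so the hesitant share may be higher and the dilution smaller. At 60% hesitant and 5% control conversion, the detectable effect among the hesitant is 9.1 points tested on everyone and 3.5 points tested in the hesitant. Also, the 35% and 76% figures are for a binary contrast. The SAP's test uses four stages, and its power for a 5-point shift ran from 59% to 84% over assumed stage splits.

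**Conclusion.** The point holds as a low-cost improvement. The between-arm test leaves unused a baseline measurement that the survey already collects.

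If about 40% are hesitant and the video acts mainly by converting them, the binary whole-sample contrast has about 35% power for a 7.5-point gain among them, against 71% to over 99% in the baseline hesitant. Adjusting the whole-sample contrast for baseline intention helps in every scenario computed, by an amount that depends on conversion and loss: 0.355 to 0.80, 0.36 to 0.58, and 0.755 to 0.84 in the spread case. The hesitant-only gain depends on where the effect falls and reverses when retention carries about half of it.

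A reader might conclude that the trial as a whole would miss a real effect. That goes too far: the weakness is confined to the non-exploratory between-arm test, and its size rests on conversion and loss rates that the documents do not give.

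**What to change.** In SAP, Objectives 1 and 2:

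1. Keep the whole-sample between-arm comparison, as *decided to* v not, and stratify or adjust it for baseline intender status. A Cochran-Mantel-Haenszel test would serve, or a risk difference standardised over baseline status, with a 95% CI.
2. Add one pre-specified secondary comparison: among participants who were unengaged, undecided or decided not at baseline, the proportion at *decided to* after the content, video v control, as a difference with 95% CI. Give its planning basis (about 526 per arm; 80% power for 4.5 to 7.3 points at 5-20% control conversion) and its place in the test hierarchy.
3. Report intender loss by arm beside it. State that comparison 2 has only about 49% power if the effect is spread as in step 5, so it supplements the whole-sample result.

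Stratifying allocation on baseline intention is optional and possible only before enrolment. The SAP is written in the past tense, so if outcome data have already been seen, the additions should be labelled accordingly.

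**Cost:** SAP wording and one extra comparison in about 40% of the sample. No new participants, data or survey content.

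### The 1315 pairs do not follow from the protocol's own inputs, which require about 813 (about 850 with an exact or continuity-corrected test)

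*Protocol*

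**What the plan says.** The calculation is in the protocol, under Evaluating the efficacy of the video-based intervention, Methods, Sample. The baseline is that "approximately 40% of Canadians in this age group are COVID-19 vaccine hesitant". The planning assumptions are given as "Estimating a 5% decrease of hesitancy in the intervention group and a correlation of about 0.45 between paired observations". From these the protocol concludes that "the intervention group requires a sample size of 1315 pairs for detecting a 5% change of marginal proportions at a power of 80" per cent, with two-sided significance of 5%. The same number is then used for the control arm, giving 2630 in total. A separate sentence covers the randomised comparison: "Using equal size groups will allow us to detect a between group difference in vaccine intentions of 5-6% with a power of 0.8", again two-sided at 5%.

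The protocol gives no formula, software, discordant proportion, continuity correction or allowance for loss. The SAP (Objectives 1 and 2) has no sample-size calculation, but it fixes the pre-post analysis: "To estimate the pre-to-post intervention change in vaccine intentions we used a binary outcome", intenders against non-intenders, tested with McNemar's chi-squared test.

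**The concern.** For paired proportions, the two marginal proportions and their correlation determine how many participants change category, and that discordant proportion together with the target difference determines the number of pairs. The protocol supplies every quantity needed, so its answer can be checked directly. A correlation of 0.45 should cut the required number well below what uncorrelated observations would need (about 1474 pairs), yet 1315 is only slightly below that.

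This number sets the enrolment, and the sentence is the only power statement for the pre-post objective. If it is inconsistent, a reader cannot tell whether the correlation, the 5 points, the 80% or the 1315 is wrong. That affects how a null pre-post result would be read, and what correlation another team would carry into its own planning.

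**Working it through.** **Inputs** (protocol, Sample):
- Hesitancy before: p1 = 0.40.
- Hesitancy after: p2 = 0.35. The change is read as absolute because the protocol speaks of "detecting a 5% change of marginal proportions".
- Correlation: ρ = 0.45.
- Two-sided 5%: z = 1.960. Power 80%: z = 0.8416.
- Test: McNemar (SAP, Objectives 1 and 2).

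**Discordant proportion**

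ψ = p1(1−p2) + p2(1−p1) − 2ρ√[p1(1−p1)p2(1−p2)]

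= 0.40×0.65 + 0.35×0.60 − 2×0.45×√(0.40×0.60×0.35×0.65)

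= 0.260 + 0.210 − 0.90×0.2337 = 0.2597

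This splits into 15.5% moving out of hesitancy and 10.5% moving into it; the difference is d = 0.05.

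**Pairs required**

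N = [1.960√ψ + 0.8416√(ψ − d²)]² / d²

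= [1.960√0.2597 + 0.8416√0.2572]² / 0.0025

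= (0.9988 + 0.4268)² / 0.0025 = 2.0325 / 0.0025 = 813

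Other uncorrected McNemar formulas give 808 to 816, and continuity-corrected formulas give 833 to 853. Power by full enumeration of the discordant counts:

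| Pairs | Uncorrected chi-square | Exact or continuity-corrected |
|---|---|---|
| 813 | 80.2% | 78% |
| 850 | 81.9% | 80.1% |
| 1315 | 94.7% | 94.1% |

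The stated 1315 is therefore not reproduced: 1315/813 = 1.62 and 1315/850 = 1.55. With 1315 pairs and ρ = 0.45, the formula reaches 80% power at a change of 3.9 points.

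**Can rounding of the inputs explain it?**
- Correlation 0.40 to 0.50 at a 40% baseline: 887 down to 740 pairs. At 1315 pairs, power is 92.7% to 96.2%, and the change detectable with 80% power is 4.1 to 3.8 points.
- Baseline 35% to 50% crossed with correlation 0.40 to 0.50: 693 to 943 pairs.
- The same grid with the change lowered to 4.5 points: at most 1164 pairs (baseline 50%, correlation 0.40).

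**Can another reading of the inputs explain it?**

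| Reading | Pairs |
|---|---|
| 0.45 as a tetrachoric correlation (ψ = 0.334) | 1047 |
| Correlation of zero | 1474 |
| 0.45 as the discordant proportion | 1411 |
| 5% as a relative fall (40% to 38%) | 5139 |
| A rise from 40% to 45% | 848 |
| One-sided test | 640 |

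None gives 1315.

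**What would give 1315?** With the other inputs held, any one of these:
- a correlation of about 0.11 (ψ about 0.42);
- a target change of about 3.9 points;
- power of about 95% (1344 pairs, within 3%);
- an allowance for loss of 1 − 813/1315 = 38%, or 1 − 850/1315 = 35%.

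Neither document states any of these.

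**Between-group statement.** For a binary intention outcome with 1315 per arm and 40% hesitant in the control arm, power is 75.5% for 5 points and 89.0% for 6 points. 80% power falls at about 5.3 points, which agrees with the protocol's range of 5 to 6. A full 5-point difference would need 1471 per arm, so 1315 is not that calculation either.

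**The case against.** The strongest reply is that over-powering is not established. It follows only if every printed input is right and 1315 is the slip. If the correlation was misprinted and was really near 0.11, then 1315 pairs give 80% power exactly as stated. That point stands: the demonstrated fact is that the paragraph is inconsistent, and the 95% figure is conditional on 0.45.

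Secondly, the practical consequence is small. The between-group statement supports 1315 per arm by itself, so nobody is enrolled beyond what the randomised comparison can use. This also stands, and it is why the point is a reporting correction and not a case for smaller arms.

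Thirdly, the protocol refers to a full funding proposal that is not among these two documents, and the derivation may be there. That is possible, but it would not repair a sentence that lists its inputs and draws a number from them that they do not give.

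Finally, the 5% is itself rounded and is the most influential input. Lowering it to 4.5 points, together with the least favourable baseline and correlation considered, still gives no more than 1164 pairs.

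**Conclusion.** The concern holds. On the stated inputs the pre-post test needs 813 pairs, or about 850 if exact or continuity-corrected; the protocol states 1315, an excess of 62% or 55%. Taken as written, power for a 5-point change is about 95% (94.1% for the exact or corrected test) instead of 80%, and 80% power is reached at about 3.9 points.

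This rests on reading the 5% as an absolute change, 0.45 as the ordinary correlation between two binary responses, and McNemar's test as named in the SAP. The cause cannot be identified from the two documents. If the printed inputs are correct, the error is in the safe direction and a null pre-post result would be more informative than readers are told. It does not affect the validity of any test or estimate, and it gives no ground for cutting the arms. It should be fixed because it is the stated derivation of the enrolment and the sole power basis for the pre-post objective.

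**What to change.** Keep 1315 per arm. Correct the pre-post sentence in one of two ways:

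1. State what was actually used to reach 1315: the formula, the discordant proportion or correlation, the target change, and any allowance for loss.
2. If the sponsor confirms 0.45 and 5 points, say that 1315 pairs give about 95% power for a 5-point change, or 80% power for about 3.9 points.

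The first is preferable if the original calculation can be found, because the second assumes that 0.45 is right. The SAP describes its analyses in the past tense, so a restated figure should be marked as a correction to the planning paragraph.

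The between-group statement can stay as the support for 1315 per arm, with a note that it is a binary-outcome figure (80% power at about 5.3 points from 40%), whereas in the SAP "we estimated the between group difference in vaccine intentions using the four-stage PAPM outcome and the Pearson Chi-Squared Test".

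The cost is the wording of one paragraph, with no change to enrolment, tests or estimates.

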Dynata will send invitations in various forms (e.g., e-mail invitations, text messages and in-app alerts) to recruit eligible participants from their existing panel (individuals who have signed with Dynata and have expressed willingness to receive invitations to various appropriate surveys) until recruitment goals and quotas are met. For recruitment purposes only, Dynata collects IP addresses as an identifier to make sure that the same person is not recruited for the same study multiple times. IP addresses are not retained by Dynata after the study and are not shared with the researchers. Dynata has identifying socio-demographic information that allows them to use our inclusion and exclusion criteria to recruit eligible participants. None of this information is communicated to the research team. Please refer to the "confidentiality" section for Dynata's privacy policies.

An electronic consent form describing the study goals and procedure will be provided at the start of the survey, after which participants will be asked whether they consent to taking part in the survey. Once they click on the icon that states they agree to participate, consent will be implied. The information collected for the survey is completely anonymous. If they decline, the survey will be terminated.

Procedure

Stratified randomization will be used to allocate participants to either: 1) intervention condition: viewing a 2-minute altruism-eliciting video, or 2) control condition: reading a text containing information (from the Public Health Agency of Canada website: <https://www.canada.ca/en/public-health/services/diseases/2019-novel-coronavirus-infection/prevention-risks.html>) about general health behaviours and public health recommendations concerning COVID-19 e.g. hand hygiene and respiratory etiquette, wearing non-medical masks, physical distancing, etc. Within each stratum (first language, sex, population density and household income), participants will be allocated randomly using a 1-to-1 ratio (1 to the intervention condition and 1 to the control condition).

The online survey will be approximately 10 minutes in length and will be available in both French and English. After reading the introductory statement of the study, participants will

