Further, if the participants have any additional questions or comments related to this survey, they may contact the principal investigator or the study coordinator, as indicated at the beginning of the survey before providing consent. Participants will also be provided at the beginning of the survey with the contact numbers for the Local Commissioner of Complaints & Quality of Services at the JGH.

At the end of the survey, participants will also be provided with a list of online resources about the COVID-19 vaccines:

- National Advisory Committee on Immunization (NACI) <https://www.canada.ca/en/public-health/services/immunization/national-advisory-committee-on-immunization-naci/recommendations-use-covid-19-vaccines.html>
- Public Health Agency of Canada (PHAC) https://www.canada.ca/en/public-health/services/diseases/coronavirus-disease-covid-19/vaccines.html?utm_campaign=hc-sc-covidvaccine&utm_medium=sem&utm_source=ggl&utm_content=ad-text-

[en&utm_term=%2Bcovid%20%2B19%20%2Bvaccine&adv=2021-0051&id_campaign=12088104441&id_source=116538480476&id_content=491971664630](https://www.dynata.com/?utm_term=%2Bcovid%20%2B19%20%2Bvaccine&adv=2021-0051&id_campaign=12088104441&id_source=116538480476&id_content=491971664630)

Inconvenience

Inconveniences involve time commitment of about 10 minutes. There will be no additional inconveniences as the survey will be filled out online, and as such they are not required to travel to our lab.

Benefits

Participants will not receive any direct personal benefit from participating in this study; however, the research results from this survey will be used to inform public health authorities on promoting COVID-19 vaccine uptake, especially among younger Canadians between ages 20-39.

Compensation

Compensation will be handled by the survey company Dynata, who is responsible for the data collection. Dynata's compensation options allow panelists to redeem from a large range of gift cards, points programs (e.g., Aeroplan), charitable contributions, and partner products or services (e.g., Hertz). All compensation is awarded only once the survey is completed. This study will compensate approximately \$2.50-\$3 depending on the way the respondent chooses to use their rewards.

Confidentiality

All data in this study will be collected online. Participants will be informed that the information collected as part of the survey will be confidential and that their participation is anonymous to the research team.

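### The between-arm test uses only people who answered after exposure and ignores baseline PAPM stage, so quitting that depends on both arm and baseline intention would bias it; adjusting for baseline stage corrects this and adds power.

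*Protocol*

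**What the plan says.** The Protocol's Procedure section (efficacy study) sets this order: sociodemographic questions, PAPM stage, a 2-minute video or a brief text according to allocation, content questions, then PAPM stage again. The content questions are there "to ensure that participants paid attention, participants will answer questions about the contents to check their understanding". No consequence is attached to failing them.

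Under Sample, "the intervention group requires a sample size of 1315 pairs", and the total is twice that, 2630, with no allowance for dropout. Under Recruitment Strategy, invitations continue "until recruitment goals and quotas are met". Under Compensation, "All compensation is awarded only once the survey is completed".

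The SAP (Objectives 1 and 2) tabulates the four stages by group at baseline and post-intervention and uses McNemar's test for change within each group. For the arms: "Post intervention, we estimated the between group difference in vaccine intentions using the four-stage PAPM outcome and the Pearson Chi-Squared Test". There is no covariate.

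Neither document defines an analysis set, gives a rule for missing post-intervention answers, or plans to report quitting by arm.

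**The concern.** A person who leaves during the video, the text or the content questions has a baseline stage but no outcome, so the Pearson test cannot include them. It therefore compares completers, whether or not quitters are replaced.

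The two exposures differ in format and subject. The video is aimed at vaccine intention, while the text covers general COVID-19 precautions. It is plausible that they lose different kinds of people. If so, the completers in the two arms differ in baseline intention before any effect of the video, and an unadjusted test on the post-intervention stage reads part of that imbalance as effect. The design aims at a difference of only 5–6 points, so a shift of one to three points matters. The variable that would correct for it has been collected from everyone before exposure and is not used.

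**Working it through.** **Inputs from the Protocol (Sample).** "approximately 40% of Canadians in this age group are COVID-19 vaccine hesitant", so 60% are intenders. "Estimating a 5% decrease of hesitancy in the intervention group and a correlation of about 0.45 between paired observations". There are 1315 per arm, "at a power of 80% and two-sided significance of 5"%.

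**The plan's own figures.** The between-arm figure reproduces: 60% v 65.3% needs 1307 per arm. With 1315 per arm, power is 75.5% at 5 points, 80.3% at 5.3 and 89.0% at 6. The paired figure does not reproduce. From 40%, 35% and 0.45 the discordant probabilities are 0.1549 and 0.1049, and McNemar's formula gives 813 pairs. That is a separate matter and errs towards a larger sample.

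**Assumed quitting.** No rates are documented. Let q be the quit rate in an arm and h the hesitant share of quitters. Baseline hesitancy among completers is (0.40 − q·h)/(1 − q).

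| Case | Video | Text | Baseline gap |
|---|---|---|---|
| A: 10% v 5%, h = 0.6 | (0.40 − 0.060)/0.90 = 0.3778 | (0.40 − 0.030)/0.95 = 0.3895 | 1.17 points |
| B: 10% v 3%, h = 0.7 | (0.40 − 0.070)/0.90 = 0.3667 | (0.40 − 0.021)/0.97 = 0.3907 | 2.41 points |
| C: 15% v 5%, h = 0.7 | (0.40 − 0.105)/0.85 = 0.3471 | (0.40 − 0.035)/0.95 = 0.3842 | 3.72 points |

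**Carrying the gap to the post-intervention stage.** With no effect and equal pre and post margins, the regression of post on baseline hesitancy has slope equal to the correlation r, so bias = r × gap.

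For the planned four-stage test, assume the split within non-intenders is unchanged. The noncentrality is then bias²/(2 × 0.40 × 0.60/1315), with 3 degrees of freedom and critical value 7.81.

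| Case | Bias, r = 0.45 | Noncentrality | False positives | Bias, r = 0.8 | Noncentrality | False positives |
|---|---|---|---|---|---|---|
| A | 0.53 | 0.08 | 5% | 0.94 | 0.24 | 6% |
| B | 1.08 | 0.32 | 7% | 1.92 | 1.02 | 12% |
| C | 1.67 | 0.77 | 10% | 2.97 | 2.42 | 23% |

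If hesitant people leave the text arm more often instead, the sign reverses.

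**Unequal quitting alone.** With quitting of 20% (video) and 5% (text) in every stage, a simulation of the four-stage test (10,000 runs, assumed split 8/22/10/60%) gave 5.2% false positives and no shift.

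**Adjusting for baseline.** In simulations of case B with r = 0.45 and intenders v non-intenders as outcome, adjustment cut the bias from 1.1 to 0.0 points and type I error from 8.4% to 4.6%.

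**Power without quitting, 40% v 35%.**
- Unadjusted SE = √[(0.40 × 0.60 + 0.35 × 0.65)/1315] = 0.01886. Then 0.05/0.01886 − 1.96 = 0.69, which is power of about 75.5%.
- Adjusted SE ≈ 0.01886 × √(1 − 0.45²) = 0.01684. Then 0.05/0.01684 − 1.96 = 1.01, which is power of about 84%.
- Simulation gave about 74% and 83%. Both comparisons use the binary outcome, so the gain comes from adjustment alone.

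**Keeping quitters at baseline stage.** Take case B, r = 0.45, and hesitancy drifting from 40% to 38% in both arms. The slope is 0.45 × √(0.38 × 0.62/0.24) = 0.446. Quitters would have had post hesitancy of 0.38 + 0.446 × (0.70 − 0.40) = 0.514, but are counted at 0.70. The excess of 0.186 applies to 10% of one arm and 3% of the other: 0.186 × 0.07 = 1.3 points against the video.

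**The case against.** The strongest reply is that the documents are silent here rather than wrong, and that the harm depends on quit rates nobody has stated. Much of this stands.

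- A reader might infer that quitters are replaced until 1315 completed pairs per arm are reached. The word pairs, the absence of a dropout allowance and payment on completion point that way. But the recruitment sentence does not define its goal, and the total is given simply as participants. The bias does not depend on replacement.
- A reader might infer that unequal quitting is itself enough to create a false effect, or that it must favour the video. Neither follows: the 20% v 5% case leaves the error rate alone, and no document supports a direction.
- A reader might carry the whole baseline gap into the outcome and use a binary test, reaching 1.2, 2.4 and 3.7 points with 9%, 24% and 49% false positives. That assumes a pre-post correlation of 1 and is not the planned test. The protocol's figure is 0.45. A correlation within one short session could be higher, hence the second set at 0.8.
- A reader might infer that people who fail the content questions are excluded. No such rule is stated.
- Case C is strong: 0.105/0.40 = 26% of hesitant people quit the video, against 0.045/0.60 = 7.5% of intenders. Payment only on completion discourages quitting in both arms.
- The SAP's baseline table by group would show an imbalance among those analysed, and McNemar's tests are within person, so between-arm baseline imbalance does not distort them.

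What remains is that the table does not show who left, and seeing an imbalance does not remove it from an unadjusted between-arm test.

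**Conclusion.** The point holds in limited form. The planned between-arm test is in effect an unadjusted completer comparison that discards an available baseline measure. It is biased if quitting depends jointly on arm and baseline intention, and not otherwise; the direction is open.

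Under the assumed patterns the bias is about half a point to 1.7 points at the protocol's correlation, with at most a doubling of the nominal 5% error. At 0.8 it reaches 3.0 points and about 23%. These figures rest on assumed quit rates, a 40% hesitant base, no true effect and an unchanged split within non-intenders. The documents do not support a claim that the trial's result is biased, or that the plan prescribes replacing or excluding anyone.

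The case for the change does not rest on quitting alone, since adjustment improves power even if nobody quits.

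**What to change.** Make the between-arm comparison intenders v non-intenders, adjusted for baseline PAPM stage: for example, a regression on arm and baseline stage that reports a risk difference with its confidence interval. The four-stage Pearson test can stay as a secondary description. This costs SAP wording only, because every person analysed already has a baseline stage. It will not correct quitting driven by reaction to the video, and the zero bias in the simulation follows because quitting there depended only on baseline stage.

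As support, report numbers randomised and numbers answering post-intervention, by arm and baseline stage, where partial records exist. They may not: the Protocol's Confidentiality section plans survey-server storage for three months after collection, and the SAP is dated February 2022 and written in the past tense. If results were already known when the adjusted analysis was added, say so and show both analyses.

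An analysis of all randomised participants with quitters kept at baseline stage should be a sensitivity analysis only, since it can be biased against the video.
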